| SP | Statistical Programmer |
| SUSAR | Suspected Unexpected Serious Adverse Reaction(s) |
| TFL | Tables, Figures and Listings |
| TOC | Table of Content |

Statistical Analysis Plan, Protocol Number V87_30

06 MAY 2022 Final Version 1.0

1. BACKGROUND AND RATIONALE

Pandemic influenza differs from seasonal influenza by representing a novel influenza strain, to which humans are immunologically naive, and has the potential for heavily impacting a young otherwise healthy population. If sustained human-to-human transmission were to occur with a pandemic influenza strain, global spread is likely, and morbidity and mortality could be staggering if efforts to contain the spread were not implemented quickly. Vaccination is the best option by which spread of a pandemic virus could be minimized or prevented. Vaccination efforts would be further enhanced by identification of the fewest number of vaccinations and lowest antigen dose needed for protection of segments of the population.

The present study is a post authorization commitment in Europe. The purpose of this study is to provide additional clinical data on aH5N1 in children in anticipation of an avian influenza pandemic, as agreed in the pediatric investigational plan with EMA/Pediatric Committee. This is a pediatric dose-ranging study for aH5N1 to dosages with decreased content of HA antigen and/or MF59 adjuvant (versus the licensed dosage for adults). The study is designed to evaluate the safety and immunogenicity of two vaccinations using three different amounts of aH5N1 and two different dosages of MF59 adjuvant, administered 3 weeks apart.

For further details please refer to section 1.0 of the protocol.

This plan describes all details related to the statistical analysis of the data collected in the study V87_30 and is based on protocol version 5, 24 JUN 20.

This analysis plan is compliant with ICH Harmonized Tripartite Guideline, 5 February 1998, Statistical Principles for Clinical Trials, E9; World Health Organization, WHO Technical Report, Series No. 924. 2004, Annex 1: Guidelines on Clinical Evaluation of Vaccines: Regulatory Expectations; and FDA Center for Biologics Evaluation and Research (CBER) Guidance for Industry, May 2007, Clinical Data Needed to Support the Licensure of Seasonal Inactivated Influenza Vaccines.

Statistical Analysis Plan, Protocol Number V87_30

06 MAY 2022 Final Version 1.0

2. OBJECTIVES

2.1 Primary Objectives

2.1.1 Primary Safety Objective

To evaluate the safety in each study vaccine group from Day 1 through Day 387, by total population and by age cohort.

2.1.2 Primary Immunogenicity Objective

To assess by total population and by age cohort, the antibody responses to each of the study vaccines prior to (Day 1) and at 3 weeks after the first or second vaccination (Day 22 or Day 43), as measured by HI and MN assays.

2.2 Secondary Objectives

2.2.1 Secondary Immunogenicity Objective(s)

To evaluate in each study vaccine group, by total population and by age cohort, the persistence of antibody responses to the H5N1 vaccine strain 6 months after the second vaccination (Day 202) as measured by HI and MN assays.

2.3 Exploratory Objectives

To further evaluate the antibody responses to seasonal, and/or homologous and/or heterologous pandemic influenza strain(s) by vaccine group on Days 1, 22, 43, and 202, as measured by HI, MN, or SRH assays (depending on availability of adequate sera and on assay availability).

3. STUDY DESIGN

This randomized, observer blind, multi-center clinical trial evaluates the immunogenicity in healthy children ages 6 months to <9 years of 6 vaccine regimens utilizing 6 different formulations including either 1.875, 3.75, or 7.5 μ g HA of pandemic H5N1 influenza strain combined with either 0.125 mL or 0.25 mL MF59, in two intramuscular (IM) injections administered three weeks apart.

Statistical Analysis Plan, Protocol Number V87_30

06 MAY 2022 Final Version 1.0

A total number of 420 subjects will be enrolled to assure at least 150 evaluable subjects for each of the age cohorts as required by the pediatric investigational plan. Subjects <9 years will be randomized to receive either one of the six formulations in 1:1:1:1:1:1 allocation ratio, stratifying according to age cohort (6 months to < 36 months and 3 years to < 9 years of age). The distribution of all enrolled subjects across the two age cohorts should be about 50% in each.

Subjects in each study vaccine group will be scheduled to receive 2 injections of aH5N1 vaccine 3 weeks (21 Days) apart. Each subject will have two periods of study participation: Treatment Period (Day 1 to Day 43 – i.e. 21 days after second injection) and Follow-up Period (Day 44 to Day 387 – i.e. 12 months after second injection).

Blood samples for serology assessments will be collected from each subject on Day 1 (before randomization), Day 22 (before vaccination), Day 43, and Day 202.

Subject Diary Cards will be provided to subjects for recording of local and systemic reactions (solicited adverse events) for 7 consecutive days after each vaccination. All unsolicited adverse events (AEs) will be collected during the treatment period.

In the follow-up period (Day 44 through Day 387), only the following subset of unsolicited AEs and the associated concomitant medications/vaccinations will be collected and documented in the subject's eCRFs: all serious AEs (SAEs), New Onset of Chronic Disease (NOCD), AEs leading to study withdrawal, and Adverse Events of Special Interest (AESIs) (as described in section 7.1 of the current protocol). These data will be captured by interviewing the subject's parent(s) or legally authorized representative (LAR) and/or by reviewing the available medical records.

For further details please refer to section 3.0 of the protocol.

Table 1 Time and Events Table

| | | Treatment period | | | | | Follow-up period | | | |
|-------------------------------|------------------------|------------------|---------------------------|--------------|---------------------------|---------------|-------------------|-------------------|---------------|-------------------|
| Visit Type | Study Day ^a | clinic visit | Diary reminder phone call | clinic visit | Diary reminder phone call | clinic visit* | safety phone call | safety phone call | clinic visit* | safety phone call |
| | | 1 | V1 + 4 | V1 + 21 | V2 + 4 | V2 + 21 | V2 + 70 | V2 + 130 | V2 + 180 | V2+ 365 |
| | | -10/0 | -1/+1 | -1 to +7 | -1/+1 | -1 to +7 | -7 to +7 | -7 to +7 | -7 to +7 | -7 to +7 |
| | | V1 | n/a | V2 | n/a | V3 | V4 | V5 | V6 | V7 |
| Study event | | | | | | | | | | |
| study treatment | | | | | | | | | | |
| vaccination | | X | | X | | | | | | |
| screening and safety | | | | | | | | | | |
| informed consent ^b | | X | | | | | | | | |
| demographics ^c | | X | | | | | | | | |

Statistical Analysis Plan, Protocol Number V87_30

16 September 2020 Draft Version 0.2

| | | Treatment period | | | | | Follow-up period | | | | |
|--|------------------------|------------------|---------------------------|----------------|---------------------------|---------------|-------------------|-------------------|---------------|-------------------|--|
| | | clinic visit | Diary reminder phone call | clinic visit | Diary reminder phone call | clinic visit* | safety phone call | safety phone call | clinic visit* | safety phone call | |
| Visit Type | Study Day ^a | 1 | V1 + 4 | V1 + 21 | V2 + 4 | V2 + 21 | V2 + 70 | V2 + 130 | V2 + 180 | V2+ 365 | |
| | | -10/0 | -1/+1 | -1 to +7 | -1/+1 | -1 to +7 | -7 to +7 | -7 to +7 | -7 to +7 | -7 to +7 | |
| | | V1 | n/a | V2 | n/a | V3 | V4 | V5 | V6 | V7 | |
| Study event | | | | | | | | | | | |
| review of systems ^c | | X | | X | | X | | | X | | |
| clinical signs ^c | | X | | X ^d | | | | | | | |
| medical history ^{c, e} | | X | | | | | | | | | |
| physical exam ^{c, f} | | X | | X | | X | | | X | | |
| exclusion/inclusion criteria ^g | | X | | X | | | | | | | |
| randomization ^h | | X | | | | | | | | | |
| 30 minutes post injection assessment | | X | | X | | | | | | | |
| Subject Diary Card dispensed with training | | X | | X | | | | | | | |

Document #: FORM2-000092701, Ed: 3.0

Source Document #: SOP-00092497

Page 11 of 41

Statistical Analysis Plan, Protocol Number V87_30

16 September 2020 Draft Version 0.2

| | | Treatment period | | | | | Follow-up period | | | | |
|--|------------------------|------------------|---------------------------|--------------|---------------------------|---------------|-------------------|-------------------|---------------|-------------------|--|
| Visit Type | Study Day ^a | clinic visit | Diary reminder phone call | clinic visit | Diary reminder phone call | clinic visit* | safety phone call | safety phone call | clinic visit* | safety phone call | |
| | | 1 | V1 + 4 | V1 + 21 | V2 + 4 | V2 + 21 | V2 + 70 | V2 + 130 | V2 + 180 | V2 + 365 | |
| | | -10/0 | -1/+1 | -1 to +7 | -1/+1 | -1 to +7 | -7 to +7 | -7 to +7 | -7 to +7 | -7 to +7 | |
| | | V1 | n/a | V2 | n/a | V3 | V4 | V5 | V6 | V7 | |
| Study event | | | | | | | | | | | |
| Subject Diary Card reminder call ⁱ | | | X | | X | | | | | | |
| Subject Diary Card reviewed and collected ^j | | | | X | | X | | | | | |
| assess all AEs | | X | | X | | X | | | | | |
| assess SAEs | | X | | X | | X | X | X | X | X | |
| assess NOCDs, AEs leading to withdrawal, AESIs | | X | | X | | X | X | X | X | X | |
| assess relevant medications ^k | | X | | X | | X | X | X | X | X | |
| Immunogenicity | | | | | | | | | | | |

Statistical Analysis Plan, Protocol Number V87_30

16 September 2020 Draft Version 0.2

| | | Treatment period | | | | | Follow-up period | | | |
|----------------------------------|------------------------|------------------|---------------------------|--------------|---------------------------|---------------|-------------------|-------------------|---------------|-------------------|
| | Visit Type | clinic visit | Diary reminder phone call | clinic visit | Diary reminder phone call | clinic visit* | safety phone call | safety phone call | clinic visit* | safety phone call |
| | Study Day ^a | 1 | V1 + 4 | V1 + 21 | V2 + 4 | V2 + 21 | V2 + 70 | V2 + 130 | V2 + 180 | V2+ 365 |
| | Visit Window (days) | -10/0 | -1/+1 | -1 to +7 | -1/+1 | -1 to +7 | -7 to +7 | -7 to +7 | -7 to +7 | -7 to +7 |
| | Visit Number | V1 | n/a | V2 | n/a | V3 | V4 | V5 | V6 | V7 |
| Study event | | | | | | | | | | |
| serology blood draw ^l | | X ^m | | X | | X | | X | | |
| Study termination/completion | | | | | | | | | | |
| Study completion ⁿ | | | | | | | | | | X |

Statistical Analysis Plan, Protocol Number V87_30

16 September 2020 Draft Version 0.2

| | | Treatment period | | | | | Follow-up period | | | | |
|--|------------------------|------------------|---------------------------|--------------|---------------------------|---------------|-------------------|-------------------|---------------|-------------------|--|
| | | clinic visit | Diary reminder phone call | clinic visit | Diary reminder phone call | clinic visit* | safety phone call | safety phone call | clinic visit* | safety phone call | |
| Visit Type | Study Day ^a | 1 | V1 + 4 | V1 + 21 | V2 + 4 | V2 + 21 | V2 + 70 | V2 + 130 | V2 + 180 | V2+ 365 | |
| | Visit Window (days) | -10/0 | -1/+1 | -1 to +7 | -1/+1 | -1 to +7 | -7 to +7 | -7 to +7 | -7 to +7 | -7 to +7 | |
| | Visit Number | V1 | n/a | V2 | n/a | V3 | V4 | V5 | V6 | V7 | |
| Study event | | | | | | | | | | | |
| Notes: * In the exceptional case that a clinic visit is not possible due to the site being closed, with appropriate sponsor approvals a home visit may be considered. | | | | | | | | | | | |
| ^a Visit 1 (vaccination visit) is the baseline for calculating visit 2 and 3; Visit 2 is the baseline for calculation of all following visits; ^b Confirm consent form (and if applicable assent form) signed prior to any procedures. The informed consent process may be conducted earlier, but within 10 days prior to Day 1. ^c Pre-vaccination procedures may occur within 10 days prior to or within the Day 1 visit, if procedures are performed prior to Day 1 inclusion/exclusion criteria have to be rechecked, and the subject's eligibility must be confirmed prior to the Day 1 vaccination; ^d clinical signs includes weight, height and temperature measurement before the 1 st vaccination, and only temperature measurement before 2 nd vaccination; ^e Including prior and concomitant medications. ^f A physical examination will be based on a review of systems, ie, a structured interview for complaints for each organ system; ^g To be checked prior to each vaccination; ^h Randomization only to be done if baseline blood sample has been collected. ⁱ A reminder call after each vaccination should occur between 3 to 5 days following vaccination; ^j If a clinic visit is not possible, review should be completed upon return of the Subject Diary card. ^k 24 hours prior to vaccination antipyretic medication is not allowed; ^l Blood sample for serology to be taken after temperature measurement, but prior to vaccination; ^m Subjects must provide a baseline blood sample after informed consent, but before randomization, up to 10 days prior to the 1 st vaccination. ⁿ Subjects who terminate the study early should complete an early termination visit when possible. | | | | | | | | | | | |

Statistical Analysis Plan, Protocol Number V87_30

06 MAY 2022 Final Version 1.0

4. RANDOMIZATION AND BLINDING

4.1 Method of Group Assignment and Randomization

Approximately 420 subjects \geq 6 months and $<$ 9 years will be randomized to receive either one of 6 formulations of aH5N1 vaccine in a 1:1:1:1:1:1 allocation ratio, stratifying according to site and age cohort (6 months to $<$ 36 months and 3 years to $<$ 9 years). The number of subjects randomized will be approximately in an equal split between the age subgroups.

The subject will be randomized in the IRT/RTSM system. The subject will receive a unique Subject ID that will be used for all eCRFs and associated study documentation for the duration of the study. The list of randomization assignments is produced by the service provider and approved by the Sponsor according to the applicable Sponsor's Standard Operating Procedure (SOP).

The following 6 formulations will be used:

| Arm | Description |
|-----|----------------------------------|
| A | 1.875 μ g + 50% MF59 0.25 mL |
| B | 3.75 μ g + 50% MF59 0.25 mL |
| C | 7.5 μ g + 50% MF59 0.25 mL |
| D | 1.875 μ g + 100% MF59 0.5 mL |
| E | 3.75 μ g + 100% MF59 0.5 mL |
| F | 7.5 μ g + 100% MF59 0.5 mL |

4.1.1 Definition of Randomization/Vaccination Errors

The list below provides categories for errors that may occur during vaccination.

Randomization errors:

- Administered wrong kit (Subject was vaccinated with a vaccine different from the one assigned at randomization).

Statistical Analysis Plan, Protocol Number V87_30

06 MAY 2022 Final Version 1.0

Vaccination errors:

- Administered only part of the study vaccine.
- Incorrect vaccine administration
- Administered expired vaccine.
- Administered temperature deviated vaccine.

Stratification error:

- Subject randomized in the wrong stratification stratum.

Randomization and Vaccination errors are considered as major (Clinical Study Report (CSR)-reportable) protocol deviations. Stratification error will not be considered as CSR-reportable protocol deviations (PDs) as there will no impact on the actual formulation administered. Subjects will be included in analysis according to actual age subgroup.

4.1.2 Forced Randomization

Forced randomization will not be utilized in this trial.

4.2 Blinding and Unblinding

The study is designed as an observer-blind study. Vaccine preparation and administration should be completed by the designated unblinded team members. Any other subject related assessments should be performed by the principal investigator (PI) and/or blinded staff members as applicable. Sponsor personnel will remain blinded.

If a subject is unblinded during the study, it is to be documented as a as CSR-reportable PD, except for subjects unblinded by Pharmacovigilance due to suspected unexpected serious adverse reactions (SUSAR). The unblinding will be documented appropriately. The unblinded subject(s) may be excluded from the Per Protocol Set (PPS). Unblinded subjects will be included in the Full Analysis Set (FAS) and safety sets.

After the final data has been collected and the database has been locked, unblinding will take place to generate the study results.

Statistical Analysis Plan, Protocol Number V87_30

06 MAY 2022 Final Version 1.0

5. SAMPLE SIZE AND POWER CONSIDERATIONS

This is a Phase 2, dose-ranging study without inferential hypothesis testing. The total sample size to be randomized is 420 subjects equally divided for two age cohorts. This number of subjects should provide sufficiently accurate estimates of the Geometric Mean Titers (GMT) to evaluate the pediatric dose. Assuming an exclusion rate of up to 14% of subjects from the analysis, around 180 subjects per age cohort will be included in the analysis. With equal allocation to one of six vaccine groups, we expect at least 60 subjects per vaccine group and at least 30 per vaccine group and age cohort to be evaluable for the statistical analysis. No formal power calculations have been done. However, the accuracy of the estimates of the GMT's can be illustrated by the length of the 95% confidence intervals (CI). Assuming a Standard Deviation (SD) of log10- transformed Hemagglutination Inhibition (HI) titers as 0.7 (based on studies V87_25 and V87_26 in healthy elderly):

- With n=30 per dose group per age cohort; the 95% CI will be from 0.56 to 1.78 times the GMT estimate
- With n=60 per dose group; the 95% CI will be from 0.67 to 1.50 times from the GMT estimate.

In pairwise dose-group comparisons with n=60 per dose group it would be feasible to detect a difference of 2.5 in the GMT ratio with statistical power of 80% with the two sample T-test at significance level of 0.05.

Statistical Analysis Plan, Protocol Number V87_30

06 MAY 2022 Final Version 1.0

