8.7 Derived and Computed Variables

Demographics

In the case that Age and/or Body Mass Index must be recomputed for the statistical analysis:

Age will be calculated in months using the following formula:

$$\text{Integer } [12 * (\text{Date of Visit 1} - \text{Date of Birth} + 1) / 365.25]$$

Age will be calculated in years using the following formula:

$$\text{Integer } [(\text{Date of Visit 1} - \text{Date of Birth} + 1) / 365.25]$$

Statistical Analysis Plan, Protocol Number V87_30

06 MAY 2022 Final Version 1.0

Body Mass Index (kg/m²) will be calculated using the following formula:

$$\text{Mass (kg)} / \text{Height}^2 (\text{m}^2)$$

Immunogenicity

Values below the lower limit of quantification (LLOQ) will be set to half that limit. Values above the upper limit of quantification (ULOQ) will be set to the value of this upper limit.

Seroconversion based on **HI** antibodies is defined as binary variable for subjects with non-missing values pre-vaccination- and post-vaccination as:

= 1, if seroconverted (defined as a \geq 4-fold increase in titer post-vaccination in those with pre-vaccination titer above or equal the LLOQ (1:10), or a post-vaccination titer \geq 1:40 for subjects with pre-vaccination titer below the LLOQ (1:10))

= 0, otherwise

Seroconversion based on **MN** antibodies is defined as binary variable for subjects with non-missing values pre-vaccination- and post-vaccination as:

= 1, if seroconverted (defined as a \geq 4-fold increase in titer post-vaccination in those with pre-vaccination titer above the LLOQ, or a post-vaccination titer \geq 4 times the LLOQ for subjects with pre-vaccination titer below the LLOQ)

= 0, otherwise

Fold increase is defined as the post-vaccination titer divided by the pre-vaccination titer.

Geometric Mean Titer

The GMT will be calculated using the following formula:

Statistical Analysis Plan, Protocol Number V87_30

06 MAY 2022 Final Version 1.0

$$10^{\left\{ \frac{\sum_{i=1}^n \log_{10}(t_i)}{n} \right\}}$$

where t_1, t_2, \dots, t_n are n observed immunogenicity titers. The 95% confidence intervals for GMT will be calculated as $10^{\{M-t_{0.975,n-1}SE\}}$, $10^{\{M+t_{0.975,n-1}SE\}}$; where M and SE are the means and standard error of logarithm base 10 -transformed titers, respectively.

Solicited Adverse Events

For details see section 13.2

Unsolicited Adverse Events

All AEs will be characterized according to the date of occurrence related to the vaccination as follows:

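### The stated precision of the GMTs (SAP 5, protocol 8.5) uses the normal quantile where SAP 8.7 prescribes t, and 30 per cell and 60 per group are expected sizes, not floors

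*SAP*

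**What the plan says.** SAP section 5 and protocol 8.5 carry the same figures. On numbers, "The total sample size to be randomized is 420 subjects equally divided for two age cohorts". Then: "Assuming an exclusion rate of up to 14% of subjects from the analysis, around 180 subjects per age cohort will be included in the analysis". From this, the sections expect at least 60 evaluable subjects per vaccine group and "at least 30 per vaccine group and age cohort to be evaluable for the statistical analysis".

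On precision, both sections state that there was no formal power calculation and offer confidence-interval lengths as an illustration: "Assuming a Standard Deviation (SD) of log10- transformed Hemagglutination Inhibition (HI) titers as 0.7", with the value taken from two studies in healthy elderly. Two lines follow: "With n=30 per dose group per age cohort; the 95% CI will be from 0.56 to 1.78 times the GMT estimate" and "With n=60 per dose group; the 95% CI will be from 0.67 to 1.50 times from the GMT estimate". Neither section names the quantile. A further sentence says that a GMT ratio of 2.5 between two groups of 60 is detectable with 80% power by a two-sample t-test at the 0.05 level.

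The method that will be used is in SAP 8.7: "The 95% confidence intervals for GMT will be calculated as" 10 to the power M ∓ t(0.975, n−1) × SE, where M and SE are the mean and standard error of the log10 titers. Protocol 8.4.2.3 describes log10 transformation and back-transformation but names no quantile.

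**The concern.** Two points in the section do not match the rest of the plan.

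- **Quantile.** The two lines say what the interval will be, so they should follow from the SAP's own interval formula. They do not, and each of the four printed limits is off in the favourable direction.
- **Cell size.** A reader takes a phrase of the form 'at least 30 per vaccine group and age cohort' as a floor for each of the 12 cells (6 formulations × 2 age cohorts). The arithmetic behind it is that of an average at the assumed exclusion rate.

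The trial tests no hypothesis and sets no success criterion, and GMTs by formulation and age cohort belong to the primary immunogenicity objective. The interval factors are therefore part of the stated support for 420 children being enough, and they are the only precision figure given at cell level.

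**Working it through.** **Inputs.** SD 0.7 on the log10 scale, n = 30 and 60, 420 randomised and exclusion up to 14% (SAP 5); two-sided 95% interval with t(0.975, n−1) (SAP 8.7); about 35 randomised per vaccine group in each age cohort (protocol 3.1), hence 70 per group.

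**1. Reproducing the stated factors.** Factor = 10^(∓ q × 0.7/√n), where q is the quantile. The standard errors are 0.7/√30 = 0.1278 and 0.7/√60 = 0.0904.

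- n=30, q = 1.96: 10^(∓0.2505) = 0.562 and 1.780. Stated: 0.56 and 1.78.
- n=60, q = 1.96: 10^(∓0.1771) = 0.665 and 1.504. Stated: 0.67 and 1.50.

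Both lines match to two decimals. A t quantile with pooled residual degrees of freedom (348) gives 0.561 to 1.784 at n=30, which would also match, but 0.664 to 1.506 at n=60, which rounds to 0.66 to 1.51 and does not. Of the variants tried, only 1.96 reproduces both lines.

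**2. The SAP 8.7 formula.**

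| n | t(0.975, n−1) | t × SE | Factors with t | Stated | Log-scale width, t relative to 1.96 |
|---|---|---|---|---|---|
| 30 | 2.045 | 0.2614 | 0.548 to 1.826 | 0.56 to 1.78 | 1.043 |
| 60 | 2.001 | 0.1808 | 0.659 to 1.516 | 0.67 to 1.50 | 1.021 |
| 27 | 2.056 | 0.2769 | 0.529 to 1.892 | none | 1.049 |

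**3. Cell and group sizes.** At exactly 14% exclusion, 210 × 0.86 = 180.6 per cohort, 35 × 0.86 = 30.1 per cell and 70 × 0.86 = 60.2 per group. Over the trial, 420 × 0.86 = 361 evaluable children, against the 12 × 30 = 360 needed for every cell to hold 30. At the ceiling there is one child to spare.

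To see what this means for single cells, assume exactly 35 randomised per cell and independent exclusions at a common rate. The evaluable number in a cell is then Binomial(35, 1 − rate), and in a group Binomial(70, 1 − rate). P(all 12 cells ≥ 30) is the single-cell probability to the 12th power; at 14% this is 0.635^12 = 0.004. Groups are treated in the same way, to the 6th power.

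| Exclusion rate | Mean cell | P(one cell ≥ 30) | P(all 12 cells ≥ 30) | Median smallest cell | P(all 6 groups ≥ 60) |
|---|---|---|---|---|---|
| 14% | 30.1 | 64% | 0.4% | 27 | 5% |
| 10% | 31.5 | 87% | 18% | 29 | 58% |
| 5% | 33.25 | 99% | 92% | 31 | 99.6% |

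**4. The power sentence.** With n=60 per group and SD 0.7, log10(2.5) = 0.398 and the standard error of the difference is 0.7 × √(2/60) = 0.1278, so the noncentrality is 3.11. The two-sided t-test on 118 degrees of freedom then has power of about 87%. Power is still 80% at n=50. The stated 80% is conservative.

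**The case against.** The strongest reply is that nothing turns on this, and much of that reply stands.

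- **The quantile effect is small.** The upper factor moves from 1.78 to 1.83 and from 1.50 to 1.52. The SD is a planning value from elderly adults applied to children. Keeping 1.96, an SD of 0.65 or 0.75 would move the n=30 upper factor to 1.71 or 1.86, at least as far as the correction does. The reported intervals will in any case be computed under SAP 8.7 from the actual data. This limits the importance of the error but does not make the printed factors right. The t form appears only in the SAP, so protocol 8.5 conflicts with SAP 8.7 rather than with the protocol's own text.
- **The numbers are worded as an expectation under a ceiling.** The section says what is expected with exclusion of up to 14%. Read that way, an expected cell size of at least 30 is true: 30.1 at the ceiling and more below it. This stands. The wording still does not tell the reader that single cells can fall short.
- **The n=30 line is conditional on n=30.** The point about averages does not make that line wrong; only the quantile does.

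A reader might go further and infer that the smallest cell will almost certainly miss 30. The documents support that only at the 14% ceiling; at 5% exclusion all 12 cells would probably reach it. A reader might also infer that the whole section overstates precision, or that these two lines are its only illustration. Neither holds, because the power sentence is a further illustration and errs in the cautious direction.

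**Conclusion.** The point holds as a minor correction. By the plan's own formula the factors should read 0.55 to 1.83 at n=30 and 0.66 to 1.52 at n=60. That 1.96 was used is inferred from the match. That the printed factors differ from SAP 8.7 is plain arithmetic.

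The figures of 30 and 60 are defensible as expected sizes at no more than 14% exclusion, but not as minimums for each cell or group. How often a cell would fall short depends strongly on the exclusion rate actually seen, which the documents bound but do not predict, so the result is a range and not a single probability. That range assumes exactly 35 per cell and independent exclusions. Allocation is only approximately 35 per cell and is also stratified by site, so some further imbalance is possible.

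The documents do not support the conclusion that the sample size is inadequate: the trial is descriptive and the shift in precision is small.

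**What to change.** In SAP section 5 and protocol 8.5:

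1. Restate the factors with t(0.975, n−1): 0.55 to 1.83 at n=30 and 0.66 to 1.52 at n=60, and name the quantile.
2. Replace the sentence on evaluable numbers with wording such as: *on average at least about 60 per vaccine group and about 30 per vaccine group and age cohort if no more than 14% are excluded; individual cells may be smaller.* The condition should stay, because a bare 'about 30' would understate the expected numbers if fewer are excluded.
3. Add the factor for a smaller cell: 0.53 to 1.89 at n=27, the median smallest cell at 14% exclusion.

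The cost is wording only. The stated precision becomes slightly less favourable. The number of children, the analyses and the power sentence need no change; if the sponsor wishes, the power can be restated as about 87%.
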